7.5 Safety data

All safety analyses will be performed on the safety population according to the actual treatment received.

7.5.1 Adverse events (AE)

AE term (Investigator term) will be assigned to the lowest level term (LLT), and a preferred term (PT) will be classified by a high level term (HLT), a high level group term (HLGT) and a system organ class (SOC) according to the Medical Dictionary for Regulatory Activities (MedDRA) thesaurus, version 19.1 or higher.

An adverse event will be considered as treatment-emergent (TEAE) if AE onset date is between first infusion of CER-001 and last infusion of CER-001 + 28 days, or if AE occurred before the first infusion of CER-001 but gets worse on study treatment. In case of incomplete date(s), see section 7.1.4.

An overview of the number of patients with at least one AE and the corresponding number of AEs will be presented including:

- Any AE
- Any TEAE
- Any serious TEAE
- Any severe TEAE
- Any TEAE leading to dose reduction of the study medication
- Any TEAE leading to temporary discontinuation of the study medication
- Any TEAE leading to permanent discontinuation of the study medication
- Any TEAE related to the study medication (Related = definite, probable or possible)
- Fatal AE
- Fatal TEAE
- Any coronary event (Coronary event = event for which HLGT = Coronary artery disorders)

All PT with HLGT = Coronary artery disorders will be described in the same way in a separate table.

CER-001-CLIN-009 CER-001

Note: recurring AEs (*i.e.* AEs classified with the same Preferred Term (PT)) for a given patient will be only counted once and only their most severe intensity or most severe relationship to the study medication will be described.

TEAEs will also be tabulated by System Organ Class (SOC) and PT. They will be presented according to seriousness (Serious / Not serious), severity (Mild/Moderate/Severe) and relationship with the study medication (Related / Not related). They will finally be tabulated by SOC and PT according to relationship with the study medication within severity.

The different analyses described above will be summarized overall, on the induction period and on the post-induction period (AEs that occurred during maintenance or extension phase). Assignment of AEs to periods will be performed as follows:

Period	Assignment
Induction	Start date of TEAE < date of infusion at W10
	(if day of AE is missing then impute to first of the month)
Post-induction	Start date of TEAE ≥ date of infusion at W10
	(if day of AE is missing then impute to first of the month)

TEAE leading to death, other SAE (AE leading to death excluded) and other significant AE (any events leading to dose reduction, leading to temporary/permanent discontinuation of the study medication) will also be described on an individual basis. These listings will include the following information:

- Randomization group
- Patient identifier
- Age, race, ethnicity, sex, weight at inclusion
- Investigator's reported term, preferred term
- Duration of the adverse event
- Severity
- Seriousness
- Action taken
- Outcome
- Relationship with the study medication
- Timing of onset of the adverse event in relation to last dose of study medication
- Study treatment at time of event or most recent study treatment taken
- Study drug dose in absolute amount
- Total number of infusions received

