**COMPARATOR PRODUCT:**

Standard sodium chloride solution will be used as the placebo.

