## 11 SAFETY MONITORING

### 11.1 Definitions

**Adverse Event (AE):** An adverse event is any untoward medical occurrence in a patient or clinical investigation subject administered a pharmaceutical product and which does not necessarily have a causal relationship with this treatment. An AE can therefore be any unfavorable and unintended sign (including an abnormal laboratory finding), symptom or disease temporally associated with the use of a medicinal (investigational) product, whether or not considered related to the medicinal (investigational) product. Pre-existing conditions which worsen during a study are to be reported as AEs.

In clinical studies, an AE can include an undesirable medical condition occurring at any time, including screening or wash-out periods, even if no experimental treatment has been administered.

**Treatment Emergent Adverse Events (TEAE):** Treatment emergent adverse events are defined as adverse events which occur during or after the administration of the first dose of the investigational medicinal product (IMP) or if present before the first administration of IMP, worsen on study treatment.

**Adverse Drug Reaction (ADR):** An adverse drug reaction is any untoward and unintended response to a medicinal product related to any dose administered.

**Unexpected Adverse Drug Reaction:** Any adverse drug reaction the nature, severity or outcome of which is not consistent with the applicable product information.

In this study, the reference document to be used to evaluate the unexpectedness of the adverse drug reactions consists in *section 5.7 Possible Adverse Reactions*” of the Investigator's Brochure (most recent version).

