12.1 Tables and graphs templates	
12.2 List of Tables, Graphs and Listings	

CER-001-CLIN-009

List of abbreviations and specialized terms:

AE	Adverse Event
ANCOVA	ANalysis of COVAriance
ATC	Anatomic Therapeutic Class
вмі	Body Mass Index
CI	Confidence Interval
CRF	Case Report Form
CRO	Contract Research Organization
DSMB	Data and Safety Monitoring Board
FPFV	First Patient First Visit
HLGT	Highest Level Group Terms
HLT	Highest Level Terms
ICH	International Conference on Harmonisation
LOCF	Last Observation Carried Forward
LPFV	Last Patient First Visit
LPLV	Last Patient Last Visit
MedDRA	Medical Dictionary for Regulatory Activities
МІ	Multiple Imputation
mITT	modified Intention-To-Treat
MRI	Magnetic Resonance Imaging
MVWA	Mean Vessel Wall Area
MVWV	Mean Vessel Wall Volume
PP	Per Protocol
PT	Preferred Term
Q1	1 st quartile
Q3	3 rd quartile
SAE	Serious Adverse Event
SAP	Statistical Analysis Plan
SOC	System Organ Class
SOP	Standard Operating Procedure
TBR	Target to Background Ratio
TFL	Tables Figures Listings
WHO-DD	World Health Organisation Drug Dictionary

CER-001-CLIN-009 CER-001

Introduction

The Statistical Analysis Plan (SAP) was developed from the following documents:

- Protocol (version 3.0 dated 13DEC2016)
- Case Report Form (CRF, version 18.2 on 30MAY2017)
- The International Conference on Harmonization (ICH) topics E3 (July 1996) [1] and E9 (September 1998) [2].

Analyses described throughout this document were planned before database lock. All analysis decisions were made prior to unblinding as well.

This SAP supersedes the protocol. Changes to the protocol (if any) will be reported in section *10 Modifications with respect to the protocol*. Finally, additional analyses not planned in this document should be clearly mentioned in the appropriate section of the clinical study report.

1. Study objectives

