6.1 Analysis populations of patients

The statistical analysis will be based on the three populations defined below. To be part of a population, patients should have signed informed consent and fullfill all inclusion / exclusion criteria. Some criteria have been added after the start of the study. Hence patients included before will be considered as compliant to these criteria via a Not Applicable (NA) status.

Safety population

The safety population will comprise all randomized patients who received at least one dose of study medication.

Safety analysis will be performed on the safety population according to the actual treatment received.

Modified Intent-To-Treat (mITT) population

The mITT population will comprise all randomized patients for whom at least one of the following conditions is satisfied:

- 3T-MRI assessment available at baseline (W0) and at least one post-baseline 3T-MRI assessment available
- 18FDG-PET/CT assessment available at baseline (W0) and at least one post-baseline 18FDG-PET/CT assessment available

Per Protocol (PP) population

The PP population will comprise all patients of the mITT population without any major protocol deviations (*Cf.* section 6.3).

Defining study populations and excluding patients from the analysis will be a joint decision taken by Sponsor and ICTA PM' representatives (Statistician and Project Leader). Patients to be excluded and

CER-001-CLIN-009 CER-001

reasons for their exclusion will be discussed during data review meetings, before database lock and unblinding.

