7.1.4 Management of missing or incomplete data

Previous and concomitant medications

For the purposes of determining whether a medication was taken during the conduct of the study, any missing or partial start or stop dates for which a definitive determination cannot be made will result in that medication will be assumed to be concomitant, to be conservative.

Linear Mixed Model

Missing data handling for assessing efficacy endpoints using linear mixed model will be described in section 7.4.1.

Adverse Events (AE)

If part of the date/time of an AE is missing, but the existing parts allow determination of timing of AE onset/end relative to start and stop date of the study drug, then the AE will be classified (treatment-emergent or not treatment-emergent) per review of the existing parts of the date/time field. If timing of the AE onset/end relative to start and stop date of the study medication cannot be made, then the AE will be assumed to be a Treatment-Emergent Adverse Event (TEAE).

Vital signs, physical examination, ECG and laboratory values

For absolute, relative changes and shifts from baseline (W0), in case of missing data for the baseline value, the latter will be replaced by the value obtained at screening visit.

CER-001-CLIN-009 CER-001

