7.7 Listings of individual data

All collected data and derived variables used for the statistical analysis will also be presented in individual patient listings, in accordance with ICH appendix 16.2. Each patient will be identified in these listings by his/her unique patient number.

8. Interim analyses

No interim analysis is planned.

9. Data and Safety Monitoring Board

The Data and Safety Monitoring Board (DSMB) will formally review unblinded study safety data to ensure there is no avoidable increased risk for harm to patients. Analyses for the DSMB meetings will be performed by an independent statistician (different from the one who will perform the final analysis). A specific SAP displays the safety data generated needed for the DSMB review.

10. Modifications with respect to the protocol

Analysis of efficacy endpoints

Statistical analysis of the primary and secondary outcomes (changes from baseline) were modified with respect to the protocol. In order to gain in terms of power, model will be fitted using all observations available for each patient during the study. Hence, linear mixed model with repeated measures will be used instead of analysis of covariance, Changes from baseline for a specified outcome could therefore be estimated at different time points based on the same model.

CER-001-CLIN-009 CER-001

11. Approval of the Statistical Analysis Plan

ICTA PM	SPONSOR
Project Manager:	Sr VP Clinical Development & Operations:
[name]	[name]
Date:	Date:
Signature:	Signature:
Biostatistician:	
[name]	
Date:	
Signature:	
Head of Medical and Scientific Development:	
[name]	
Date:	
Signature:	

CER-001-CLIN-009

12. Appendices

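### SAP 7.5.1 ties treatment-emergent status to CER-001 infusions, so read literally no dated new-onset double-blind event on placebo qualifies by onset; correct the anchor before database lock

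*SAP*

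**What the plan says.** SAP 7.5.1 gives a two-limb rule. Under the onset limb, an event is treatment-emergent if "AE onset date is between first infusion of CER-001 and last infusion of CER-001 + 28 days". The worsening limb adds a second route: "or if AE occurred before the first infusion of CER-001 but gets worse on study treatment". Both limbs start from CER-001, although the second also refers to study treatment in general.

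Elsewhere the documents use a different anchor:

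- SAP 7.1.4, on incomplete dates, works from the dates of study drug or study medication. Where timing "relative to start and stop date of the study medication cannot be made", the event is assumed to be treatment-emergent.
- SAP 6.1: "The safety population will comprise all randomized patients who received at least one dose of study medication".
- Protocol 11.1 counts "adverse events which occur during or after the administration of the first dose of the investigational medicinal product (IMP"), plus earlier events that worsen on treatment. It sets no end date. Protocol section 9, headed as the investigational product section, covers both CER-001 and placebo.
- The adverse event template in SAP 12.1 has a placebo column.

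On the comparator, the protocol synopsis says: "Standard sodium chloride solution will be used as the placebo". Under Protocol 6.6, everyone who accepts the extension receives CER-001, whichever arm they came from.

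On precedence, the SAP Introduction says: "This SAP supersedes the protocol". SAP section 10 declares one change: "Statistical analysis of the primary and secondary outcomes (changes from baseline) were modified with respect to the protocol". It says nothing about the TEAE definition.

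**The concern.** A patient given saline has no first or last infusion of CER-001 during the double-blind phase. The onset limb therefore gives that patient no window in which a new event can count, although the placebo column is there for comparison.

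Safety and tolerability over 24 weeks is a primary objective, and over 48 weeks a secondary one. The TEAE flag drives most rows of the AE overview, the tables by system organ class and preferred term, and the induction and post-induction tables. It also drives the individual listing of deaths, which SAP 7.5.1 limits to TEAEs leading to death. A programmer who followed the text would produce a between-arm safety comparison in which one arm can register ordinary new-onset events and the other cannot.

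**Working it through.** The point concerns a definition, so the plan has no figure to reproduce. The check applies the rule to the planned schedule.

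**Inputs.** 30 patients at 2:1 (Protocol 6.4), so 20 on CER-001 and 10 on placebo. Double-blind infusions run from W0 to W48 (Protocol 6.1). There are 12 open-label infusions every two weeks up to W72 (Protocol 6.6), so the first is at W50. Full completion is assumed.

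**Onset limb, double-blind phase.** Possible onset days from W0 to W48: 48 × 7 + 1 = 337.

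| Patient | First to last CER-001 infusion | Window with 28 days added | Days W0–W48 covered |
|---|---|---|---|
| CER-001, no roll-over | W0–W48 | W0–W52 (52 weeks) | 337 of 337 |
| CER-001, roll-over | W0–W72 | W0–W76 (76 weeks) | 337 of 337 |
| Placebo, no roll-over | none | none | 0 of 337 |
| Placebo, roll-over | W50–W72 | W50–W76 (26 weeks) | 0 of 337 |

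In planned patient-weeks, the window covers 0 of 10 × 48 = 480 on placebo and all of 20 × 48 = 960 on CER-001. To W24, the primary safety period, it covers 0 of 240 and 480 of 480. With the anchor moved to study medication, all 337 days qualify in both arms.

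**Worsening limb.** It needs an event that began before the first infusion of CER-001. For a placebo patient who never receives CER-001 that date does not exist, so the limb is undefined. For a placebo patient who rolls over, the date is W50, so an event that began earlier and worsened on study treatment could qualify.

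**Undeterminable timing.** Such events default to treatment-emergent under SAP 7.1.4 in either arm.

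**Illustration.** Suppose the same share of patients in each arm has a dated new-onset double-blind event, with no event entering by another route. The shares are assumptions.

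| Assumed share | CER-001, literal rule | Placebo, literal rule | Spurious difference |
|---|---|---|---|
| 20% | 4/20 | 0/10 | 20 points |
| 50% | 10/20 | 0/10 | 50 points |
| 80% | 16/20 | 0/10 | 80 points |

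With the study-medication anchor the difference is 0 points in each row.

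**Open-label time once the anchor is corrected.** If the last infusion is then read as the last open-label one, a placebo patient who rolls over has a window from W0 to W76. Of that, 76 − 50 = 26 weeks follow the start of CER-001: 26/76 = 34%. Roll-over uptake is not stated, so no arm-level share can be given.

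**The case against.** The best defence is that nobody would program this literally. The second limb already refers to study treatment, neighbouring sections use study medication, and the template expects placebo events. An almost empty placebo column beside a populated row for any AE would stand out in the table review of SAP 7.1.9. The sponsor also approves dry-runs before lock (SAP 12.2).

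This makes a slip the likely explanation and lowers the practical risk. It does not make the text right. Dry-runs come before lock and unblinding comes after it (SAP section 5), so dry-runs cannot show the true arms. Double programming covers only the primary endpoint. A correction made after unblinding would change a safety definition with treatment known.

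It is also fair to say that the coverage counts restate the definition and do not estimate harm.

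Three stronger inferences are tempting, and the documents do not support them:

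- *CER-001 must look worse in every TEAE table, whatever the truth.* The induction table can hold no dated new-onset placebo TEAE. In the overall and post-induction tables, however, open-label events of former placebo patients could enter the placebo column, so the direction there is not certain.
- *Placebo events vanish from the safety report.* The overview rows for any AE, fatal AE and any coronary event do not use the flag, and neither do the full data listings. DSMB review follows its own SAP. The individual death listing is not a safeguard: it uses the flag, and the listing of other SAEs excludes deaths. A double-blind placebo death could miss both, though the fatal AE row would show it.
- *The silence of SAP section 10 shows a concealed change.* A slip would not be listed as a change either, so the silence is equally consistent with no intended departure.

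**Conclusion.** The wording is wrong and should be corrected before lock. Confidence is high for the anchor. On a literal reading the onset limb covers 0 of 337 double-blind days on placebo and 337 of 337 on CER-001, which affects about 10 of the 30 planned patients. The result would be a strong bias towards more double-blind TEAEs on CER-001, confined to outputs that use the flag. These figures rest on the planned schedule, full completion and the 2:1 split. They describe what the text does if followed, and are not a forecast that it will be followed.

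The handling of open-label time is a separate clarification, held with medium confidence. SAP 7.5.1 describes the post-induction period as maintenance or extension, which implies an end at W48. But the assignment row and the overall summary have no upper limit, while Protocol Appendix B collects adverse events to W76.

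**What to change.** **Main change.** In both limbs of SAP 7.5.1, replace infusion of CER-001 with infusion of study medication (CER-001 or placebo). This agrees with SAP 7.1.4 and with the start point in Protocol 11.1. List the 28-day end limit in SAP section 10, since Protocol 11.1 has none. The cost is one phrase in two places, one derivation and one line in section 10. Infusion dates and event onset dates are already collected.

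**Secondary clarification.** State that, for the between-arm tables, the last infusion means the last double-blind infusion. Report events with onset on or after the first open-label infusion separately, by original arm. The separation is needed because W48 plus 28 days reaches W52, past the first open-label infusion at W50. It keeps CER-001 time in former placebo patients from being counted as placebo. This needs a small amount of extra programming and no new data.

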### 6.1 Overview of the study design and dose regimen

This is a Phase III, multi-center, randomized, 48 weeks, double-blind, parallel-group, placebo-controlled study to evaluate efficacy and safety of CER-001 on ApoA-1 and vessel wall area in patients with genetically defined familial primary hypoalphalipoproteinemia and receiving background optimized lipid therapy.

Double-blind treatment phase: After obtaining written informed consent and provided the patient fulfills the selection criteria as defined in *section 7*, he/she will be randomized to receive twenty-nine doses of CER-001 or placebo, weekly during the first 8 weeks (9 doses) and then every two weeks during the following 40 weeks (20 doses). Dosing visits will have a window of +/- 2 days around the strict weekly or biweekly date.

Open-labeled treatment phase: After obtaining written informed consent, patient will receive twelve doses of CER-001, one every two weeks during 24 weeks following the last dose administered during double-blind treatment period. Dosing visits will have a window of +/- 2 days around the strict biweekly date.

Patients will have a safety follow-up visit at least 30 days after the last dose administered.

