## 8.5 Safety Follow-up

### For patients treated until week 48:

Patients will be instructed to fast prior to the visit. A safety follow-up for all patients will be conducted 4 weeks (+/- 7 days) after the final dose of study medication and will include,

- Physical exam (See Section 8.8.1)
- Blood Pressure and Heart Rate
- Vital signs (See Section 8.8.2)
- ECG (See Section 8.8.3)
- Previous and concomitant treatments
- Adverse Events
- Urinalysis (See Section 8.8.4)
- Blood samples for
  - Serum biochemistry (See Section 8.8.4)
  - Hematology and coagulation (See Section 8.8.4)

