#### **8.7 Assessments and Procedures for Patients who Prematurely Discontinue Study Medication during double-blind treatment period**

Patients who withdraw from study medication should come to the site for a safety follow-up, 4 weeks after the last dose: the same safety assessments as the ones planned for study completer's week 52 visit (V31) should be performed.

Additionally:

- In case the study medication is stopped prematurely prior to week 24 (V18), a 3T-MRI should be performed as soon as possible after study drug discontinuation. If the patient agrees to stay in the study, he/she will be asked to come back at the site for full assessments as per protocol every 8 weeks until visit V30 and a last 3T-MRI will be performed at visit V30.
- In case the study drug is stopped during the extension treatment period (i.e. after week 24 (visit V18), patient should come back to the site for full assessments as per protocol every 8 weeks until week 48, a last 3T-MRI will be done at week 48.

All AEs (related or not related) must be reported until the final study evaluation at visit V30 and thereafter only the SAEs likely to be related to the study drug or study procedures must be notified.

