## **11.4 Adverse Event Reporting**

All observed or volunteered adverse events occurring during the study period, at any time from the signature of the informed consent until the final study evaluation, regardless of treatment group or suspected causal relationship to study drug, will be recorded on the adverse event page(s) of the eCRF.

The need to capture this information is **not dependent** upon whether the adverse event is considered to be related to the use of the study drug. Also, adverse events resulting from concurrent illnesses and reactions to concurrent medications must be reported. In order to avoid vague, ambiguous, or colloquial expressions, the AE will be recorded using standard medical terminology rather than the patient's own words.

Each AE should be described in detail in the eCRF: nature of the event (a sign, a symptom or a diagnosis preferably), onset and stop dates, severity, relationship to study drug, seriousness (see below *Section 11.5*), action taken including corrective therapy and outcome.

AEs that are believed to be at least possibly related to study drug should be followed until satisfactory resolution or acceptable stabilization.

For all AEs, the Investigator must pursue and obtain the necessary information both to determine the outcome of the adverse event and to assess whether it meets one of the criteria for classification as a serious adverse event requiring immediate notification to the **PV Department of ICTA PM** (see *Section 11.5*). For all AEs, sufficient information should be obtained by the Investigator to determine the causality of the adverse event (e.g., study drug or other illness).

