## APPENDIX A: Schedule of Assessments in double-blind treatment phase

	Screening V1	Randomization Baseline V2 W0	Period 1 Induction Infusion every week				Period 2 Maintenance Infusion every two weeks				Period 3 Extension				Period 3 Extension			Final safety V31 W52
			V3 to V5 W1 to W3	V6 W4	V7 to V9 W5 to W7	V10 W8	V11 to V13 W10 to W14	V14 W16	V15 to V17 W18 to W22	V18 W24	V19 to V21 W26 to W30	V22 W32	V23 to V25 W34 to W38	V26 W40	V27 to V29 W42 to W46	V30 W48		
Informed consent	X																	
Selection criteria	X																	
Demography	X																	
Medical history (smoking status)	X																	
Counseling on heart healthy diet and lifestyle	X																	
Vital signs	X	X		X		X		X		X		X		X		X	X	
Blood pressure & heart rate assessment	X	X		X*		X*		X*		X*		X*		X*		X*	X	
*BP and HR should be measured pre-infusion and post-infusion																		
Height	X																	
Weigh	X	X		X		X		X		X		X		X		X	X	
Physical exam	X	X		X		X		X		X		X		X		X	X	
12-lead ECG	X	X		X		X		X		X		X		X		X	X	
Adverse events 		X	X	X	X	X	X	X	X	X	X	X	X	X	X	X	X	
Previous and concomitant medications	X	X	X	X	X	X	X	X	X	X	X	X	X	X	X	X	X	
FSH 	X																	
Serum Pregnancy Test	X																	
Urinary Pregnancy Test			X		X		X		X		X		X		X		X	
Hematology/coagulation 	X	X		X		X		X		X		X		X		X	X	
Serum chemistry 	X	X		X		X		X		X		X		X		X	X	
Urinalysis 	X	X		X		X		X		X		X		X		X	X	
Markers of inflammation, oxidation and CV risk 	X	X		X		X				X							X	
Anti-ApoA-1 antibody	X					X				X							X	
Fasting plasma glucose 	X	X		X		X		X		X		X		X		X	X	
HbA1c	X	X																
Biomarkers sample		X									X							
Lipid & Lipoprotein profile  (from fastingsamples)	X	X				X					X						X	
Cholesterol Eflux 	X	X				X				X							X	
Genotyping 	X																	
Study drug infusion 			X	X	X	X	X	X	X	X	X	X	X	X	X	X	X	
Pharmacokinetics  (2 hours after starting the infusion)			X								X							
3T MRI (MVWA)			X			X					X						X	
18FDG-PET/CT (if site equipped to do it)			X								X							

1. AEs and SAEs (related or not related) to be recorded at each visit until the final study evaluation. After the end of the study, only the SAEs likely to be related to the study medication or study procedures must be notified.

2. FSH in women whose last menstrual period was between 6 and 12 months before screening

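### The SAP ends the treatment-emergent window 28 days after the last infusion; the protocol sets no end, the change is undeclared, and later events of early stoppers who stay in follow-up miss the main AE tables

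*SAP*

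**What the plan says.** **Classification.** Two places define a treatment-emergent event. Protocol 11.1 takes "adverse events which occur during or after the administration of the first dose of the investigational medicinal product", plus earlier events that worsen on treatment, and gives no closing date. SAP 7.5.1 requires that "AE onset date is between first infusion of CER-001 and last infusion of CER-001 + 28 days", with the same allowance for worsening. The SAP introduction says that it supersedes the protocol and that changes are reported in section 10. Section 10 lists only the change of efficacy model.

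**Follow-up visit.** Protocol 6.1: "Patients will have a safety follow-up visit at least 30 days after the last dose administered". Protocol 8.5: "A safety follow-up for all patients will be conducted 4 weeks (+/- 7 days) after the final dose of study medication".

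**Collection.** Protocol 11.4 records events "at any time from the signature of the informed consent until the final study evaluation", without naming a visit. The first footnote to Appendix A has "AEs and SAEs (related or not related) to be recorded at each visit until the final study evaluation", and the schedule's last column is V31 at week 52. For patients who stop drug during the double-blind period, protocol 8.7 states: "All AEs (related or not related) must be reported until the final study evaluation at visit V30". After that, only SAEs likely to be related to drug or procedures are notified. The same section also calls these patients to a safety visit 4 weeks after the last dose, with the week 52 assessments. Under 8.5 those include adverse events.

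**Use.** In SAP 7.5.1 the SOC/PT tables, with their breakdowns by seriousness, severity and relationship, contain treatment-emergent events only.

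**The concern.** Protocol 9.12 wants patients who stop drug to be followed as if they had completed treatment. Section 8.7 sets visits every 8 weeks to week 48 (by agreement if they stop before week 24). The SAP rule then takes most of that time out of the main safety tables. A patient with a last dose at week 8 leaves the window at week 12, halfway through the 24 weeks over which safety is a primary objective. If stopping differs by arm, the excluded time differs by arm too. With 30 patients randomized 2:1 (about 20 and 10), a few reclassified events can change the comparison.

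The point is where the window ends, not which product it names. I read the SAP rule as referring to study-drug infusions in either arm.

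**Working it through.** **Inputs.** 30 randomized, 24 completers and 20% discontinuation (protocol 12.4, SAP section 3); 48 weeks of double-blind treatment; window of last infusion + 28 days (SAP 7.5.1); follow-up visit at 28 ± 7 days (protocol 8.5).

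**The plan's own figure.** 24 / (1 − 0.20) = 30, which matches. The difference, 30 − 24 = 6, is the largest number of stoppers used below.

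**Early stoppers.** For a last dose at week s and follow-up to week 48, the weeks collected but not treatment-emergent are max(0, 48 − (s + 4)). The denominator is 30 × 48 = 1,440 planned patient-weeks.

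| Last dose | Excluded weeks per patient | One stays | Six stay |
|---|---|---|---|
| W8 | 36 | 36 (2.5%) | 216 (15%) |
| W16 | 28 | 28 (1.9%) | 168 (11.7%) |
| W24 | 20 | 20 (1.4%) | 120 (8.3%) |
| W36 | 8 | 8 (0.6%) | 48 (3.3%) |
| W44 or later | 0 | 0 | 0 |

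If no stopper stays, this component is zero.

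**Completers.** Under 8.5 the visit can fall on days 21 to 35, so at most 35 − 28 = 7 days per patient are collected but not counted. For 24 completers the maximum is 24 × 7 = 168 patient-days. A patient who continues on CER-001 in the open-label phase has no such gap, because the last infusion moves to as late as week 72. Under 6.1 the visit is on day 30 or later, always after the window has closed.

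**Who carries the excluded time.** Six stoppers at W24 contribute 6 × 140 = 840 days against the completers' maximum of 168, a share of 840 / 1,008 = 83%. One stopper at W16 gives 196 / (196 + 168) = 54%. One at W24 gives 140 / (140 + 168) = 45%. Early stoppers carry most of it unless very few stay or they stop late.

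**Section 8.7.** The safety visit falls at s + 4 weeks and V30 at week 48. The visit comes after V30 when s > 44. On the nominal dosing schedule that means a last dose at W46, with the visit at about W50. One sentence of 8.7 then ends full AE reporting at W48, while another requires an AE assessment at about W50. If the first is followed literally, non-serious events between W48 and W50 can go unrecorded, although they lie inside the SAP's own 28-day window.

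**The case against.** A fixed interval after the last dose is a legitimate on-drug presentation. Twenty-eight days matches the nominal 4-week visit, and long off-drug time dilutes tables meant to describe drug effects. This stands: the window may remain the main presentation. It does not excuse the undeclared difference from 11.1 or the mismatch with the visit window.

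Four stronger readings are tempting, and the documents do not support them.

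- *The plan gives four different ends to one AE window.* Only protocol 11.1 and SAP 7.5.1 classify events. Sections 8.7, 11.4 and Appendix A govern collection, and 6.1 and 8.5 govern visit timing. For most early stoppers who stay, the final evaluation is V30, so 8.7 agrees with 11.4.
- *Late events disappear.* The Any AE, Fatal AE and coronary outputs are not limited to treatment-emergent events. Other SAEs are listed patient by patient with randomization group and timing from the last dose, and SAP 7.7 lists all data. What is lost is the by-arm tabulation.
- *About 12% of patient-time is lost.* That needs six stoppers, all at W16 and all staying. Protocol 9.12 says that stopping drug alone is not discontinuation, and defines discontinuation as ceasing participation. On that definition the planned 20% leave the study and add no later follow-up.
- *A W46 stopper is covered for only two weeks.* The same section requires a safety visit with an AE assessment at about W50. The text contradicts itself; it does not settle on two weeks.

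**Conclusion.** The point holds as an undeclared narrowing of the safety definition, plus a local contradiction in protocol 8.7. It should be corrected, because safety is a primary objective and the change is cheap.

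Its size cannot be fixed from the documents, which do not say how many patients will stop drug and stay. The range runs from zero if none stay, through 2% of planned patient-weeks for one stopper at W16, to 8% to 15% if six stop between W24 and W8 and all stay. The number who stay and the stopping weeks are my assumptions. The percentages measure follow-up time; they equal shares of events only if the event rate is constant. For completers the effect is at most 7 days each. The 8.7 contradiction affects only patients whose last dose comes after W44.

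**What to change.** 1. **SAP 7.5.1.** Keep a fixed on-drug window, but make it long enough to cover the follow-up visit: last infusion + 35 days if the 8.5 visit window is kept. Tie it to the infusion date and not to attendance, so that an early or missed visit does not change its length. Add one set of SOC/PT, serious, severe and related tables by arm for all AEs from first dose to the end of double-blind follow-up, or to the first open-label infusion.
2. **SAP section 10.** Declare the difference from protocol 11.1.
3. **Protocol.** Reconcile the follow-up timing in 6.1 and 8.5. Reconcile 8.7 with 11.4 and Appendix A so that full AE reporting runs to the later of V30 and the post-dose safety visit.

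The cost is SAP wording, a protocol clarification and one extra set of tables, with no new visits. The added tables mix on-drug and off-drug time and should be labelled accordingly.
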